Complete Title: Evaluating a Marketing Campaign to Increase Participation in School Meals

Short Title: Increasing School Meal Participation

Protocol Date: July 19, 2024

NCT #: NCT06419218

Study Principal Investigator:

[name]
Stanford University
email: [contact]

Introduction

The goal of these analyses is to examine whether parental exposure to a social media campaign encouraging school meal participation increases the frequency with which children eat school lunch and school breakfast. This analysis plan pre-specifies the analyses before collecting data and therefore serves as our ex-ante planned analysis.

Study Protocol

Participants will complete a randomized controlled trial. After providing informed consent, participants will take a baseline survey programmed in Qualtrics. At the end of the survey, participants will be randomized to 1 of 2 arms: 1) school meal campaign or 2) control campaign (focused on reading, a neutral topic unrelated to school meals). In the school meal campaign arm, participants will be asked to join a private Facebook group where they will view messages about the benefits of children eating school meals. In the control arm, participants will be asked to join a private Facebook group where they will view messages about the benefits of their children reading (a neutral topic unrelated to school meals). In both arms, researchers will post messages to the private Facebook groups approximately twice per week for 6 weeks. After the 6-week campaigns end, participants in both arms will take a follow-up survey programmed in Qualtrics.

Statistical Considerations

General Principles

Primary analyses will be intent-to-treat, including all randomized participants regardless of whether they joined a Facebook group or completed the follow-up survey. Depending on the proportion of participants who join the Facebook groups, we may consider conducting secondary, per-protocol analyses including only participants who joined a Facebook group.

We will use a two-sided critical alpha of 0.05 to conduct all statistical tests. All confidence intervals presented will be 95% and two-sided.

Outcome Measures

Table 1 describes the outcome measures.

Table 1. Outcome measures

Outcome	Description	Timing of Assessment
Co-primary outcomes		
Children's consumption of school lunches	Parental report of the usual number of days per week their child ate school lunch during the past month. Assessed with 1 item: "Thinking about the last month, how many days a week did your child usually eat school lunch ?" This item will be scored on a 6-point scale from "0 days per week" (0) to "5 days per week" (5).	Collected in a ~10 minute survey at baseline and again at 6 weeks.
Children's consumption of school breakfasts	Parental report of the usual number of days per week their child ate school breakfast during the past month. Assessed with 1 item: Thinking about the last month, how many days a week did your child usually eat school breakfast ?" This item will be scored on a 6-point scale from "0 days per week" (0) to "5 days per week" (5).	Collected in a ~10 minute survey at baseline and again at 6 weeks.
Secondary outcomes		
Campaign reactions		
Noticing the school meal campaign	Parental report of whether they noticed the school meal campaign. Assessed with 1 item: "In the last 6 weeks, have you seen any messages or advertising on Facebook encouraging children to eat school lunch or school breakfast?" Response options are "yes" (1) and "no" (0).	Collected in a ~10 minute survey at 6 weeks.
Number of school meals campaign topics recognized	Parental report of the number of topics they recognize having seen in messages about school meals. Assessed with 1 item: "Which of these topics did the messages discuss, if any? Check all that apply." Response options list 8 topics plus options for "none of these" and "not sure." Number of topics recognized will be calculated as the sum of all topics that parents indicate they have seen. Those who answer, "none of these" and "not sure" will be coded as recognizing 0 topics. Those who report not noticing the school meal marketing campaign will be coded as recognizing 0 topics.	Collected in a ~10 minute survey at 6 weeks.
Frequency of reading campaign messages	Parental report of the frequency with which they read their assigned campaign messages. Assessed with 1 item: "In the past month, how often did you read these messages?" This item will be scored on a 5 point scale ranging from "Never or less than 1 time per week" (1) to "Every day or more often" (5).	Collected in a ~10 minute survey at 6 weeks.

Outcome	Description	Timing of Assessment
Social interactions about campaign	Parental report of the frequency with which they talked to others about their assigned campaign messages. Assessed with 1 item: “In the last month, how often did you talk to others about these messages?” This item will be scored on a 5 point scale ranging from “Never or less than 1 time per week” (1) to “Every day or more often” (5).	Collected in a ~10 minute survey at 6 weeks.
Social interactions about school meals	Parental report of the frequency with which they talked to others about school meals. Assessed with 3 items (e.g., “In the last month, how often did you talk to others about school meals?”). Response options are on a 5-point scale ranging from “Never or less than 1 time per week” (1) to “Every day or more often” (5). Responses to the 3 items will be averaged to create a mean score.	Collected in a ~10 minute survey at 6 weeks.
Perceived benefits of school meals		
Perceived benefits of school lunch	Parental report of the benefits of their child consuming school meals. Assessed with 8 items (e.g., “My child eating school lunch helps my child do well in school”). Response options are on a 5-point scale ranging from “Strongly disagree” (1) to “Strongly agree” (5). Responses to the 8 items will be averaged to create a mean score.	Collected in a ~10 minute survey at baseline and again at 6 weeks.
Perceived benefits of school breakfast	Parental report of the benefits of their child consuming school meals. Assessed with 8 items (e.g., “My child eating school breakfast helps my child do well in school”). Response options are on a 5-point scale ranging from “Strongly disagree” (1) to “Strongly agree” (5). Responses to the 8 items will be averaged to create a mean score.	Collected in a ~10 minute survey at baseline and again at 6 weeks.
Knowledge that school meals are free		
Knowledge that school lunch is free	Parental knowledge that lunches served at their child’s school are free to all students. Assessed with 1 item: “Are school lunches free for all students at your child’s school?” Response options “yes” (coded as 1) and “no” or “not sure” (both coded as 0).	Collected in a ~10 minute survey at baseline and again at 6 weeks.
Knowledge that school breakfast is free	Parental knowledge that breakfasts served at their child’s school are free to all students. Assessed with 1 item: “Are school breakfasts free for all students at your child’s school?” Response options “yes” (coded as 1) and “no” or “not sure” (both coded as 0).	Collected in a ~10 minute survey at baseline and again at 6 weeks.

Outcome	Description	Timing of Assessment
Perceived healthfulness of school meals		
Perceived healthfulness of school lunch	Parental perception of the healthfulness of the lunches served at their child's school. Assessed with 1 item: "How healthy or unhealthy are the school lunches at your child's school?" Response options are on a 5-point scale ranging from "Very unhealthy" (1) to "Very healthy" (5).	Collected in a ~10 minute survey at baseline and again at 6 weeks.
Perceived healthfulness of school breakfast	Parental perception of the healthfulness of the breakfasts served at their child's school. Assessed with 1-item: "How healthy or unhealthy are the school breakfasts at your child's school?" Response options are on a 5-point scale ranging from "Very unhealthy" (1) to "Very healthy" (5).	Collected in a ~10 minute survey at baseline and again at 6 weeks.
Behavioral intentions		
Intentions to encourage their children's consumption of school lunch	Parental report of the likelihood of encouraging their child to eat school lunch in the next month. Assessed with 1 item: "In the next month, how likely are you to encourage your child to eat school lunch ?" Response options are on a 5-point scale ranging from "Not at all likely" (1) to "Extremely likely" (5).	Collected in a ~10 minute survey at baseline and again at 6 weeks.
Intentions to encourage their children's consumption of school breakfast	Parental report of the likelihood of encouraging their child to eat school breakfast in the next month. Assessed with 1 item: "In the next month, how likely are you to encourage your child to eat school breakfast ?" Response options are on a 5-point scale ranging from "Not at all likely" (1) to "Extremely likely" (5).	Collected in a ~10 minute survey at baseline and again at 6 weeks.
Barriers to participation		
Barriers to children's school lunch consumption	Parental report of the barriers preventing their child from eating school lunch. Assessed with 1 item: "What are some reasons that your child doesn't eat school lunch more often? Check all of the reasons that apply."	Collected in a ~10 minute survey at baseline and again at 6 weeks.
	Response options list 15 reasons plus "NA - my child eats school lunch every day or almost every day" and a free response option for "other." Total number of barriers selected will be summed. Those who report "NA - my child eats school lunch every day or almost every day" will be coded as having 0 barriers.	

Outcome	Description	Timing of Assessment
Barriers to children's school breakfast consumption	
Parental report of the barriers preventing their child from eating school breakfast. Assessed with 1 item: "What are some reasons that your child doesn't eat school breakfast more often? Check all of the reasons that apply." Response options list 16 reasons plus "NA - my child eats school breakfast every day or almost every day" and a free response option for "other." Total number of barriers selected will be summed. Those who report "NA - my child eats school breakfast every day or almost every day" will be coded as having 0 barriers.
	Collected in a ~10 minute survey at baseline and again at 6 weeks.
Food insecurity	
Household food insecurity
 
Parental report of household food insecurity. Assessed with 6 items (e.g., "In the last month, were you ever hungry but didn't eat because there wasn't enough money for food?") Response options include "no" or "yes"; "never true", "sometimes true", or "often true"; "only 1 or 2 days," "some days but not every day," or "almost every day." Responses of "often" or "sometimes" and "yes" are coded as affirmative (yes). Likewise, responses of "almost every day" and "some days but not every day" are coded as affirmative (yes). The sum of affirmative responses to the six questions in the module is the household's raw score on the scale.
 
Household food security status is assigned as follows:
 
Raw score 0-1—High or marginal food security
 
Raw score 2-4—Low food security
 
Raw score 5-6—Very low food security
 
Analyses will dichotomize households into those with high or marginal food security and those with low or very low food security.
	Collected in a ~10 minute survey at baseline and again at 6 weeks.

Outcome	Description	Timing of Assessment
Child food insecurity	
Parental report of child food insecurity. Assessed with 8 items (e.g., “In the last month, did you ever cut the size of your child's meals because there wasn't enough money for food?”) Response options include “no” or “yes”; “never true”, “sometimes true”, or “often true”; “only 1 or 2 days,” “some days but not every day,” or “almost every day.” Responses of “often” or “sometimes” and “yes” are coded as affirmative (yes). Responses of “almost every day” and “some days but not every day” are coded as affirmative (yes). The sum of affirmative responses to the 8 questions in the module is the child's raw score on the scale.
 
Child food security status is assigned as follows:
 
Raw score 0-1—High or marginal food security among children
 
Raw score 2-4—Low food security among children
 
Raw score 5-8—Very low food security among children
 
Analyses will dichotomize households into those with children with high or marginal food security and those with children with low or very low food security.
	Collected in a ~10 minute survey at baseline and again at 6 weeks.

Data Preparation

To prepare the data, we will examine all scales to ensure they achieve adequate internal consistency (Cronbach's $\alpha > 0.70$), dropping items as needed to improve internal consistency. If we are unable to achieve adequate internal consistency by dropping items, we may exclude the unreliable scales from analyses (e.g., not analyze treatment effects on these outcomes).

Statistical Methods

1. Analyses of the co-primary outcomes:

- a. We will use mixed effects regression models to **evaluate the effect of the school meals campaign on children's school lunch consumption and children's school breakfast consumption**. In separate models for lunch and breakfast, we will regress usual number of school meals eaten per week on an indicator variable for trial arm (school meal campaign vs. control), an indicator variable for time period (baseline vs. follow-up) and the interaction between trial arm and time period. The treatment effect is given by the coefficient on the interaction term. We will consider linear or Poisson models, based on the distribution of the outcome and model fit. We will treat the intercept as random to account for repeated measures within participants and will include state fixed effects.
- b. To **examine the potential differential effects of the school meals campaign by demographic characteristics**, analyses will examine whether the effect of the school meals campaign on children's school lunch consumption and children's school breakfast consumption is modified by household income (\leq vs. $>185\%$ Federal Poverty Level) or parent's race/ethnicity (with categories determined based on distribution of race/ethnicity in the sample). We will test for effect modification by adding to the primary model three-way interactions (i.e., difference-in-difference-in-differences) between trial arm, time period, and variable(s) for the potential effect modifier, using separate models for each outcome (school lunch consumption and school breakfast consumption) and effect modifier (income and race/ethnicity).

2. Analyses of the secondary outcomes:

- a. We will use a similar mixed effects regression approach to **evaluate the effect of the school meals campaign on secondary outcomes** (e.g., perceived benefits of school meals, knowledge and attitude about school meals, behavioral intentions, perceived barriers to school meal participation, and food insecurity). We will use mixed effects logistic regression for binary outcomes, mixed effects linear regression for continuous outcomes, and mixed effects Poisson regression for count outcomes. We will treat the intercept as random to account for repeated measures within participants. For outcomes measured only at follow-up (e.g., noticing), we will use linear, logistic, or Poisson regression.

Sample Size Needs

We estimated power using G*Power 3.1.¹ No published studies have examined the effect of parent-directed school meal marketing campaigns on children's school meal consumption,² so we powered to detect a small standardized effect (Cohen's $f=0.05$, equivalent to $d=0.10$).³ We assumed 75% of the initial sample of 800 parents would complete the follow-up survey (similar retention to a previous study using similar methods⁴), yielding an analytic sample of $n=600$. Assuming $\alpha=0.05$ and a correlation among repeated measures of 0.60 (based on prior research⁵), a sample of this size would yield 80% power to detect an effect of school meal campaign on consumption of school lunch and consumption of school breakfast of $f=0.05$ or larger. Our prior studies with parents suggest that messaging interventions are likely to yield effects of this size or larger.⁶⁻⁸ Additionally, studies of child-directed school meal marketing campaigns⁹ and multicomponent interventions that include marketing^{10,11} suggest effects of this size are reasonable.

Exclusions and Outliers

We will exclude participants who do not consent or do not complete the baseline survey, as these participants will not be randomized. Primary analyses will be intent-to-treat, including all randomized participants regardless of whether they join their assigned Facebook group or complete the follow-up survey. We will also consider conducting a secondary analysis per-protocol, examining only those who joined their assigned Facebook group and completed the follow-up survey.

References

3. Cohen J. *Statistical Power Analysis for the Behavioral Sciences*. Academic press; 2013.

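### The optional per-protocol analysis has two definitions and no rule for running it, and it selects on joining after randomisation: fix one definition, label it non-randomised, and prefer a complier estimate (minor)

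*Combined protocol and SAP*

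**What the plan says.** The combined protocol and SAP describes the per-protocol analysis in two places.

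- Statistical Considerations, General Principles: "we may consider conducting secondary, per-protocol analyses including only participants who joined a Facebook group". The sentence opens with a condition, "Depending on the proportion of participants who join the Facebook groups", but gives no proportion.
- Exclusions and Outliers: the analysis is again something to consider, now "examining only those who joined their assigned Facebook group and completed the follow-up survey", with no condition on the joining proportion.

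Under Study Protocol, randomisation comes at the end of the baseline survey. Parents are then asked to join a private Facebook group on school meals or, in the other arm, the "control campaign (focused on reading, a neutral topic unrelated to school meals").

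Both sections make ITT on all randomised parents the primary analysis. Statistical Methods, 1a, fits a mixed model with arm, time, arm by time and state: "The treatment effect is given by the coefficient on the interaction term". The scale is open: "We will consider linear or Poisson models, based on the distribution of the outcome and model fit". No model, covariates or label are given for the per-protocol analysis.

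**The concern.** Two matters are separate.

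First, the plan is meant to fix analyses before data collection, yet it leaves open which parents form the per-protocol set and whether the analysis is run. Both could be settled after the joining data are seen.

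Second, under either definition membership depends on a parent's choice after assignment. Because the groups differ in topic, parents who join a school-meals group need not resemble those who join a reading group. The arm-by-time model removes stable level differences between the two sets of joiners. It does not remove differences in how much they would have changed anyway, or regression to the mean if joining depends on the baseline report. A reader could take the joiners-only result as the randomised effect of taking part, and the plan offers no estimate for joiners that keeps the randomised comparison.

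**Working it through.** **Inputs from Sample Size Needs.** "We assumed 75% of the initial sample of 800 parents would complete the follow-up survey", giving 600; "a correlation among repeated measures of 0.60"; two-sided alpha 0.05; f = 0.05.

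**Assumptions.** 1:1 allocation (300 completers per arm); joining p = 40 / 60 / 80%; retention independent of joining; the primary model on a linear scale, approximated by change scores; unit outcome SD. The documents give no joining rate, selection correlation or outcome SD in days.

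**The plan's own figure.** For the within-between interaction, λ = N·m·f²/(1 − ρ) = 600 × 2 × 0.0025 / 0.40 = 7.5, so power is 78.1% against the stated 80%: reproduced within 2 points. In this formula f = 0.05 corresponds to a difference in change of 0.20 SD, which is used below as an illustrative joiner effect.

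**Do the two definitions matter numerically?** The first keeps 800p = 320 / 480 / 640 parents and the second 600p = 240 / 360 / 480. The extra parents have baseline data only. Under random loss, the SD of the difference between the two estimates is 0.4 × √[2(1/(300p) − 1/(400p))] = 0.026 / 0.021 / 0.018, where 0.4 = 1 − 0.60. The joiners-only SE is 0.894 × √(2/(300p)) = 0.115 / 0.094 / 0.082, with 0.894 = √(2 × 0.4). The difference is small beside the SE.

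**Joiners-only bias with no true effect.** If a normally distributed tendency to join is cut at rate p, the selection factor is k = φ(z_p)/p = 0.966 / 0.644 / 0.350. With equal join rates:

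- selection on change: k × (difference between arms in correlation) × (change per SD of readiness to change);
- selection on baseline: −(1 − 0.60) × k × (difference between arms in correlation).

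| Assumed case | 40% | 60% | 80% |
|---|---|---|---|
| Change; meals arm only; correlation 0.3–0.5, slope 0.1–0.2 | +0.03 to +0.10 | +0.02 to +0.06 | +0.01 to +0.04 |
| Change; correlations differ by 0.1, slope 0.1–0.2 | 0.010–0.019 | 0.006–0.013 | 0.003–0.007 |
| Baseline; meals arm only; correlation 0.1–0.3 | −0.04 to −0.12 | −0.03 to −0.08 | −0.01 to −0.04 |
| Same selection, same join rates | 0 | 0 | 0 |

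The baseline row changes sign if joining falls, rather than rises, with baseline days.

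**Same selection, unequal join rates.** At 50% joining in the meals arm and 70% in control, k = 0.798 and 0.497, a difference of 0.301. Selection on change gives 0.301 × (0.03 to 0.10) = 0.009 to 0.030 SD. Selection on baseline gives −0.4 × 0.301 × (0.1 to 0.3) = −0.012 to −0.036 SD. Equal selection alone therefore does not remove the bias.

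**Scale.** Joiners-only 95% half-widths are 1.96 × SE = 0.226 / 0.185 / 0.160. The largest tabulated bias is 0.4 × k × 0.3 = 0.116 / 0.077 / 0.042, or 51% / 42% / 26% of the half-width. It would raise the false-positive rate from 5% to about 17 / 13 / 8%. This is not a ceiling: if joining correlates 0.1–0.3 directly with change, in the meals arm only, at 70% joining, the bias is (0.1 to 0.3) × 0.497 × 0.894 = 0.04 to 0.13 SD.

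**Complier estimate.** Adjusting for baseline, the residual SD is √(1 − 0.36) = 0.80.

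| | 40% | 60% | 80% |
|---|---|---|---|
| SE = 0.80 × √(2/300)/p | 0.163 | 0.109 | 0.082 |
| 95% half-width | 0.32 | 0.21 | 0.16 |
| Power, 0.20 SD joiner effect | 0.23 | 0.45 | 0.69 |
| Power, 0.10 SD joiner effect | 0.09 | 0.15 | 0.23 |
| Joiners-only power, 0.20 SD, if unbiased | 0.41 | 0.56 | 0.69 |

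The ITT half-width is 0.128 with the same baseline adjustment and 0.143 on change scores. The complier estimate is that adjusted ITT divided by p, so it has the same power.

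**The case against.** The strongest case is that little turns on this. ITT is primary in both places; the other analysis is called secondary and per-protocol and is only to be considered. The groups are private and arm-specific, so joining a group and joining the assigned group are almost the same thing, and under random loss the two sets give nearly the same estimate. The reading arm has a parallel joining step, which should make selection more alike. The larger biases assume selection in one arm and none in the other, and the cases can have opposite signs. All of this stands, and it is why the point is minor. It does not supply a single definition or a rule for running the analysis, and with different topics neither equal selection nor equal join rates can be assumed.

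A second objection is that a complier estimate is only a rescaled ITT, and that an adjusted linear ITT shown beside it gives each co-primary outcome another chance of significance. The rescaling is conceded: the gain is an effect for joiners that rests on the randomised comparison, not power. The risk is real. With no effect, the planned and adjusted ITTs disagree on significance about 3.7% of the time, and at least one is significant about 6.9% of the time. The adjusted ITT must therefore be barred from use as a test.

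A reader might infer that the joiners-only result would overstate the campaign's effect. The documents do not support that: they give nothing that fixes the sign, and selection on baseline can push it either way.

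**Conclusion.** The point holds as a minor, inexpensive improvement. The two definitions conflict, no joining threshold is given, and either set is a non-randomised comparison. The joiners-only contrast can be biased if joining relates to change or to the baseline report differently by arm, or if the same selection operates with unequal join rates. Under the tabulated inputs the bias runs from near zero to about 0.12 SD at 40% joining. Those inputs are assumptions, so its actual size and sign are unknown.

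Two stronger readings should be resisted. A reader might infer that the conflicting definitions would produce materially different results; under random loss they would not, although loss related to outcome could separate them. A reader might also infer that the trial's main conclusion is at risk; the primary ITT does not use joining status and is unaffected.

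**What to change.** 1. Use one definition in General Principles and in Exclusions and Outliers, for example joined the assigned group, fitted with the primary mixed model. State in advance whether the analysis is run, or at what joining proportion. Label it non-randomised, and report join and retention rates by arm.

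2. Make a complier average causal effect, for lunch and for breakfast, the preferred secondary estimate of the effect of joining: two-stage least squares in days per week, arm as instrument for joining the school-meals group, adjusted for baseline days and state, robust SE. State its assumptions: no control access to the meals group; no effect of assignment on non-joiners; no effect of the reading campaign on school meals; no spillover; follow-up missing at random given arm, baseline and state.

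3. If a linear ITT with the same adjustment and parents is shown beside it, say that it is for scaling only and is not a second test of the co-primary outcomes. The planned mixed-model ITT, linear or Poisson, stays the only primary analysis.

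The cost is a few lines of SAP text, two short models per outcome and by-arm reporting. Join status must be recorded, which the planned per-protocol analysis already needs. The downsides should be stated: the complier interval is wider than the ITT interval; its power is no greater than that of the equally adjusted ITT; and it divides any dropout bias by the join rate. For example, if dropout is selective in the meals arm only, an assumed ITT bias of 0.01–0.04 SD becomes 0.03–0.11 / 0.02–0.07 / 0.02–0.05 SD at 40 / 60 / 80% joining.

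### Social interactions about school meals could be measured at baseline but is collected only at 6 weeks, which gives up precision that a baseline covariate would recover

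*Combined protocol and SAP*

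**What the plan says.** In the combined protocol and SAP, Table 1 lists five secondary outcomes under Campaign reactions, all with the timing "Collected in a ~10 minute survey at 6 weeks". Four are defined by the campaign or its messages:

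- noticing: "Parental report of whether they noticed the school meal campaign"
- topics recognized: "Parental report of the number of topics they recognize having seen in messages about school meals"
- reading: "Parental report of the frequency with which they read their assigned campaign messages"
- talking to others about the assigned campaign's messages.

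The fifth, Social interactions about school meals, is defined as "Parental report of the frequency with which they talked to others about school meals". It has three items, of which one is shown. That item asks about the last month and does not mention the campaign. "Responses to the 3 items will be averaged to create a mean score".

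The 12 secondary outcomes outside this group (two each for benefits, knowledge, healthfulness, intentions, barriers and food insecurity) are collected at both surveys.

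Statistical Methods 2a gives outcomes measured twice a random-intercept mixed model, similar to the primary model in 1a, where the treatment effect is the arm-by-time interaction. For the rest: "For outcomes measured only at follow-up (e.g., noticing), we will use linear, logistic, or Poisson regression". No covariates are named for these regressions, and the plan names no imputation method.

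**The concern.** A follow-up-only schedule is natural for a question about messages that parents have not yet seen. It is not needed for a question about talking to others about school meals, which a parent can answer before randomization. The plan gives no reason for treating this outcome differently from the 12 that are measured twice.

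Without a baseline, the analysis cannot remove the stable differences between parents in how much they talk about school meals, so the standard error is larger than it needs to be. There is also no baseline value of this outcome with which to compare parents who complete follow-up and those who do not, when a quarter are expected to be lost. A baseline that was not collected cannot be recovered after randomization.

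**Working it through.** **Inputs.** From Sample Size Needs: 800 parents, 75% retention, hence 600 completers and 200 lost; correlation ρ = 0.60 between repeated measures, given for lunch and breakfast consumption. From General Principles: two-sided alpha 0.05. Assumptions: equal allocation (the ratio is not stated), so 300 completers and 400 baselines per arm; the same SD at both surveys; and ρ = 0.60 carried over to this outcome, with a range shown because the plan gives no value for it.

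**The plan's own figure.** For the co-primary outcomes, the within-between interaction test has noncentrality f²·N·m/(1 − ρ) = 0.0025 × 600 × 2 / 0.4 = 7.5. With F(1, 598) this gives power 0.781, within 2 points of the stated 80%. The inputs are therefore read as the plan uses them.

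**Variance per arm for this outcome, in SD² units:**

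- Follow-up only (as planned): 1/300.
- Arm-by-time interaction, completers only: 2(1 − ρ)/300.
- Arm-by-time interaction, all 800 baselines: (1 − ρ²)/300 + (1 − ρ)²/400.
- Baseline score as covariate: (1 − ρ²)/300.

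Multiplying by 300 gives the variance relative to follow-up only. At ρ = 0.60:

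- interaction, completers: 2 × 0.4 = 0.80
- interaction, all baselines: 0.64 + 0.75 × 0.16 = 0.76
- baseline covariate: 1 − 0.36 = 0.64.

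**Standard error and detectable effect at ρ = 0.60.** Follow-up only: SE = √(2/300) = 0.082 SD; detectable effect with 80% power = 2.80 × 0.082 = 0.23 SD. Baseline covariate: SE = 0.082 × √0.64 = 0.065 SD; detectable effect 0.18 SD. Interaction with all baselines: 0.20 SD. Power at an illustrative effect of 0.20 SD is 68.8%, 86.5% and 80.2% respectively.

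**Range over ρ** (variance relative to follow-up only):

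| ρ | Interaction, all baselines | Baseline covariate |
|---|---|---|
| 0.30 | 1.28 | 0.91 |
| 0.40 | 1.11 | 0.84 |
| 0.50 | 0.94 | 0.75 |
| 0.60 | 0.76 | 0.64 |
| 0.70 | 0.58 | 0.51 |

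**Break-even for the interaction model.** Setting (1 − ρ²) + 0.75(1 − ρ)² = 1 gives ρ² + 6ρ − 3 = 0, so ρ = −3 + √12 = 0.46. Below that value, collecting a baseline and then fitting the interaction model gives a less precise estimate than the planned follow-up regression. The covariate analysis never does worse, because 1 − ρ² cannot exceed 1.

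**Parents lost to follow-up.** In the interaction model at ρ = 0.60, the 200 baseline-only parents lower the relative variance from 0.80 to 0.76, a 5% reduction. Most of the gain comes from the completers' own baselines.

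**The case against.** The strongest reply is that this is a legitimate scheduling choice. The outcome sits under Campaign reactions, the follow-up-only analysis is pre-specified, and randomization protects the contrast; chance imbalance is already reflected in its standard error. Other school-meal measures taken at baseline could inform the handling of dropout. The correlation of 0.60 is borrowed. All of this stands and limits the point to one of precision in one of 17 secondary outcomes.

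Two qualifications also stand. First, the distinction between this outcome and the other four rests on Table 1's definitions. The noticing item, as worded, asks about any Facebook messages promoting school meals and could itself be put to parents at baseline. Second, two of the three social-interaction items are not shown, so answerability before randomization is known for one item only.

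A reader might infer three stronger things that the documents do not support:

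- *That the schedule breaks the intent-to-treat commitment.* The statement about "including all randomized participants regardless of whether they joined a Facebook group or completed the follow-up survey" is made for primary analyses and does not bind this outcome.
- *That leaving out the parents without follow-up is a major loss.* They would have no follow-up value under either schedule, and their baselines add little, as shown above.
- *That moving the outcome into the same mixed model as the other school-meal secondaries delivers the 36% reduction.* That figure belongs to baseline adjustment. The interaction model gains 24% at ρ = 0.60 and loses 11% at 0.40.

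**Conclusion.** The point holds as a modest design improvement. The plan does not contradict itself here, and the planned analysis is not biased by design, although dropout could bias it as it could any analysis of completers. The size of the gain depends on a correlation that the documents do not give for this outcome. The figures also assume equal allocation, the planned retention and equal SDs at the two surveys. The direction of the gain is secure only for baseline adjustment; with the unconstrained interaction it depends on whether ρ exceeds about 0.46. A secondary benefit is a baseline value with which to assess whether dropout is related to prior level. No co-primary result is affected. This is an optional, cheap improvement.

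**What to change.** 1. Add the social-interaction items that do not refer to the campaign to the baseline survey, and change this outcome's timing in Table 1 to both surveys. If one of the two items not shown refers to the campaign, keep it at follow-up only and define the adjusted score from items asked twice.
2. In Statistical Methods 2a, specify for this outcome either a linear regression of the 6-week score on arm with the baseline score as covariate, or a mixed model that constrains the arms to be equal at baseline. Do not use the unconstrained arm-by-time interaction. If that model is kept for uniformity with the other secondaries, state that the gain is smaller and may be negative.
3. Leave the four outcomes defined by the campaign or its messages at follow-up only.

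The cost is up to three more items in a survey of about 10 minutes that already covers school meals, plus two text edits. The added burden should be slight, though the documents do not quantify it. Any priming would be equal across arms, because randomization comes at the end of the baseline survey. If enrolment has already begun, report this outcome as a follow-up-only contrast among completers, and name in advance any available baseline covariates to be used for it.
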